4.6.1.1 Treatment duration

Summaries of dosing, treatment duration, dose interruptions or reductions during the randomized double-blind treatment period will be provided for each treatment arm separately.

The overall treatment duration (weeks), including and excluding dose interruptions, will be summarized descriptively by treatment arm. The overall treatment duration including dose interruptions will be defined as follows:

[Date of last positive dose of randomized treatment received (pirfenidone/placebo) – date of first intake of randomized treatment) + 1)] / 7.

The overall treatment duration excluding dose interruptions will be derived from the treatment administration panels using the time windows described above, considering only days on treatment. i.e. positive dose.

Details on treatment administration, reductions or interruptions will be listed.

4.6.1.2 Doses and Dose modifications or interruptions

The total dose (mg), the average daily dose (mg/d) and the last dose administered (mg/d) will be presented descriptively for each of the study treatments.

The average daily dose will be calculated by summing up the number of capsules taken, divided by the overall treatment duration including dose interruptions as defined above.

Numbers and proportions of patients with at least one dose modification, or drug interruption, will be presented for each treatment arm separately. Numbers and proportions of patients with 1, 2, 3 or more dose modifications, or treatment interruptions, will be given.

Pirfenidone — F. Hoffmann-La Roche Ltd

The total number of dose modifications, reductions or treatment interruptions, will be presented together with numbers and frequencies of reasons for dose modification, reduction or treatment interruption.

Dose modifications, reductions or treatment interruptions will be presented as given in the drug logs dose strength and number of capsules taken.

In addition, dose intensity will be analyzed descriptively by treatment arm over time. For calculation of dose intensities, the time from first administration of randomized treatment to the end date of randomized treatment will be considered. The following formula will be used for calculation:

Dose intensity (DI) = (total dose received / total dose planned)*100.

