Following treatment initiation, the daily dosage will be titrated to the full dosage of nine capsules per day over a 14-day period. After the titration period, trial treatment will continue through Week 24 and monitoring will be conducted by site visits. Patients should remain on a stable maintenance dose for the duration of the treatment period unless the dose is reduced or dosing is interrupted to manage an adverse event (see CSP Section 5.1.1). Any patient with an actual or anticipated interruption of trial treatment for a period of ≥28 consecutive days will be reported by telephone to Roche's medical monitor or designee to discuss the circumstances of the case. A Follow-up Visit will occur 28 days after the end of the 24-week double-blind treatment period.

After completion of the double-blind treatment period and the Follow-up visit at Week 28, patients will be given the opportunity to receive open-label pirfenidone within a safety follow-up period of up to 12 months of the trial protocol. A final Follow-up visit will be performed at the end of the safety period, 28 days after the last open-label dose. During the safety follow-up period, the patients should be evaluated by the investigator initially at monthly visits during the first 6 months and subsequently at each visit occurring approximately every 3 months thereafter.

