4.2 TRIAL PERIODS, OBSERVATION AND ANALYSIS TIMES

Where durations are to be calculated (e.g. treatment duration), these will be derived based on the interval in days (end date – start date + 1) and converted to months and years if needed, using 30.4375 and 365.25, respectively, as denominator if not otherwise specified.

For the investigational medicinal product (IMP) exposure, treatments administered from the date of first randomized pirfenidone/placebo treatment up to the date of completion of double-blind treatment or date of early treatment discontinuation, will be regarded.

For drug safety, analyses will be restricted to AEs or assessments that occurred from the first day of randomized treatment until the date of last positive dose of randomized treatment plus 28 days.

Safety analyses for the 12-month follow-up period will be performed using the time window from the safety follow-up period start up to the study completion/discontinuation visit.

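### The average daily dose is labelled mg/d but defined as capsules divided by weeks, so at full dose the written formula gives 63 instead of 2403.

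*SAP*

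**What the plan says.** SAP version 3.0, section 4.6.1.2, sets out the dose summaries and their units: "The total dose (mg), the average daily dose (mg/d) and the last dose administered (mg/d) will be presented descriptively for each of the study treatments". It then gives the rule for the second of these: "The average daily dose will be calculated by summing up the number of capsules taken, divided by the overall treatment duration including dose interruptions". The rule refers back to the definition of duration already given.

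That definition is in section 4.6.1.1, which fixes the unit: "The overall treatment duration (weeks), including and excluding dose interruptions, will be summarized descriptively by treatment arm". The formula takes the date of last positive dose, subtracts the date of first intake and divides by seven; it ends "date of first intake of randomized treatment) + 1)] / 7".

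Section 4.2 has a general rule that durations are counted in days and "converted to months and years if needed, using 30.4375 and 365.25, respectively, as denominator if not otherwise specified". For treatment duration, 4.6.1.1 does specify otherwise.

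The same formula and the same duration definition stand in SAP version 2.0 (sections 4.7.1.1 and 4.7.1.2), so the wording passed through a revision unchanged.

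**The concern.** Two units are wrong, each independently of the other. The numerator is a count of capsules and is never turned into milligrams. The denominator is in weeks, although the statistic is a daily dose. The quotient is capsules per week under a heading of mg/d.

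This sentence is the plan's only definition of the statistic. A programmer who follows it gets a wrong value for every treated patient in both arms. One who produces the labelled quantity has to depart from the plan, and an independent check programmed from the SAP text would then disagree with the table. The definition also carries forward: SAP 4.7 has open-label exposure analysed in the same way as in the double-blind period, for treatment duration and amount of drug taken. (That section cites 4.7.1, which is the version 2.0 numbering; in version 3.0 exposure is in 4.6.1.)

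**Working it through.** **Inputs**

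- Full dosage: nine capsules per day (SAP 2).
- Capsule strength: 267 mg (Protocol 4.3.1.1).
- Full daily dose: 2403 mg (Protocol 4.3.2.1).
- Titration: 3 capsules per day on days 1 to 7, 6 per day on days 8 to 14, 9 per day from day 15 (Protocol 3.1, Table 2).
- Double-blind course: 24 weeks, or 168 days.

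**The plan's own figure.** 9 capsules × 267 mg = 2403 mg/d, which matches the protocol exactly.

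**The formula as written.** Let C be the total capsules taken and D the days from first intake to last positive dose, inclusive. The SAP gives

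C / (D/7) = 7C/D, in capsules per week.

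At a constant nine capsules per day, C = 9D, so the result is 7 × 9 = 63 for any duration. For 168 days: 9 × 168 = 1512 capsules, and 1512/24 = 63.

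**The labelled quantity.** 267C/D, in mg/d. For the same patient: 1512 × 267/168 = 2403 mg/d.

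**Ratio.** (267C/D) / (7C/D) = 267/7 = 38.14. C and D cancel, so the factor does not depend on duration, interruptions or dose reductions.

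**Partial corrections, at full dose**

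| Numerator | Denominator | Result |
|---|---|---|
| capsules | weeks | 63 capsules/week |
| capsules | days | 9 capsules/day |
| mg | weeks | 16,821 mg/week |
| mg | days | 2403 mg/d |

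Only both corrections together give the labelled quantity.

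**A complete course with titration.** Capsules: 3 × 7 + 6 × 7 + 9 × 154 = 21 + 42 + 1386 = 1449. As written: 1449/24 = 60.4. As labelled: 1449 × 267/168 = 2302.9 mg/d. The ratio is again 38.14.

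**The case against.** The strongest reply is that nobody would be misled. The sentence just before the formula gives the unit as mg/d and also calls for total dose in mg, which already needs the capsule-to-milligram conversion. The drug log records strength beside the number of capsules. An average of 63 mg/d is less than a quarter of one capsule (63/267 = 0.24) and would clash with the total dose shown alongside it. A programmer would very probably correct it, and a constant factor common to both arms would not distort a comparison between them. The item is also minor: the safety outcome measures in SAP 2.2.4 name dose reductions and interruptions, not average daily dose; SAP 4.6 plans no formal testing of safety parameters; and total dose, last dose, treatment duration and dose intensity do not use this formula. Finally, constant full dosing for 168 days is not a course the trial allows, because titration is required.

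Most of this stands as a limit on the consequence. The documents do not show that any table is wrong, and 60.4 against 2302.9 mg/d is the more realistic pair for a full-course patient. None of it repairs the text. The days default in SAP 4.2 cannot, because the formula points to a named quantity that 4.6.1.1 defines in weeks. Nor can the label, since a label that contradicts its formula shows the intention but leaves the definition wrong.

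**Conclusion.** The concern holds. The average daily dose as defined in SAP 4.6.1.2 is in capsules per week and cannot be the mg/d quantity it is labelled as. The written formula understates the intended figure by a factor of 267/7 = 38.1 for every patient.

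This rests on reading the back-reference to duration as the weekly definition in 4.6.1.1, which is the only definition of that quantity, and on the 267 mg capsule strength. For placebo the milligrams are nominal, since those capsules contain no pirfenidone. The error is confined to a descriptive exposure summary and its open-label counterpart and touches no efficacy result or adverse-event count. It should be corrected, but it does not threaten the trial's conclusions.

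**What to change.** Replace the sentence in SAP 4.6.1.2 with an explicit formula:

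average daily dose (mg/d) = (total capsules taken × 267 mg) / (date of last positive dose − date of first intake + 1), with the denominator in days.

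Add that the milligrams are nominal for placebo. Since SAP 4.6.1 excludes unknown doses from the exposure analyses, also say whether days with an unknown dose stay in the denominator. In SAP 4.7, correct the cross-reference from 4.7.1 to 4.6.1 so that the open-label summary uses the same formula.

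SAP 4.5.8 says the primary analysis was performed in March 2019, so the sponsor should also confirm which formula the existing exposure tables used and rerun them if it was the written one.

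The cost is a one-line correction and a short check of the exposure program. No dose, clinical rule or data collection changes.

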4.6.2 Adverse Events

Verbatim descriptions of adverse events (AEs) will be mapped to a preferred term (PT) and system organ class (SOC) using the Medical Dictionary for Regulatory Agencies (MedDRA®). MedDRA version 20.1 or above and related SMQ lists will be used for coding.

AEs will be graded according to the National Cancer Institute Common Terminology Criteria for Adverse Events (NCI CTCAE), Version 4.03. For AEs of varying severity, the most severe grade as documented on the eCRF will be used in the summaries. An AE will be considered severe if the most extreme grade will be larger or equal to 3.

After informed consent has been obtained but prior to initiation of trial treatment, only serious adverse events caused by a protocol-mandated intervention (e.g. invasive procedures such as biopsies, discontinuation of medications) should be reported. All adverse events will be reported until 28 days after the last dose of study drug. After this period, the Investigator should report any SAEs that are believed to be related to prior study drug treatment.

For safety analysis of the double-blind treatment period treatment-emergent adverse events (TEAEs) will be defined as:

• AEs that started or worsened on or after first intake of randomized treatment until last positive dose of randomized treatment + 28 days

Adverse events that are reported after informed consent but before the first intake of randomized treatment will be considered as non-treatment-emergent AEs. These might include AEs that occur during the screening period.

Post-treatment AEs are not expected to occur, but will be defined as AEs that are reported more than 28 days after the last dose of randomized treatment for patients who do not enter the 12-month safety follow-up period. Those AEs will be listed.

Pirfenidone — F. Hoffmann-La Roche Ltd

The analysis of AEs within the framework of the primary study analysis will focus on treatment-emergent AEs (TEAE).

An overview of patient safety profile will present the number and proportion of patients in each treatment arm experiencing:

- Any and any related treatment-emergent adverse events (TEAE)
- Any and any related serious treatment-emergent adverse events (serious TEAE)
- Any and any related severe treatment-emergent adverse events (TEAEs ≥ Grade 3)
- Any and any related TEAE of special interest (AESI). Adverse events of special interest for this trial include the following:

Cases of potential drug-induced liver injury that include an elevated ALT or AST in combination with either an elevated bilirubin or clinical jaundice, as defined by Hy's law: [ALT or AST >3 x ULN + total bilirubin >2 x ULN]

- Any and any related hepatic side effects: elevations in ALT and AST >3 × ULN at the same timepoint in the study.
- Any and any related gastrointestinal (GI) disorder (MedDRA SOC: GI Disorders)
- Any and any related photosensitivity (MedDRA Preferred terms Nodular rash, Photodermatosis, Photosensitivity reaction, Pruritus, Pruritus generalized). Potential updates in those terms will be needed in case the MedDRA version changes.
- Any and any related rash (MedDRA Preferred terms Rash, Rash erythematous, Rash generalized, Rash macular, Rash maculo-papular, Rash papular, Rash pruritic, Solar dermatitis, Solar urticarial, , Sunburn, Erythema, Dry skin). Potential updates in those terms will be needed in case the MedDRA version changes.
- Angioedema (MedDRA preferred term Angioedema).
- Dizziness (MedDRA preferred term Dizziness).
- Fatigue (MedDRA preferred term Fatigue).
- Weight loss (MedDRA preferred term Weight loss).
- Increase in QT interval: In the event of a QTcF interval of >500 ms or an increase from baseline of >60 ms, a repeat ECG must be obtained within 24 hours.
- Any and any related TEAE leading to death
- Any and any related TEAE leading to treatment discontinuation

Pirfenidone — F. Hoffmann-La Roche Ltd

- Any grade 3-4 laboratory liver test results
 - o ASAT (SGOT) results
 - o ALAT (SGPT) results
 - o alkaline phosphatase results
 - o total bilirubin results

The incidence of TEAEs, related TEAEs, non-serious TEAEs, serious TEAEs, related serious TEAEs, grade 3-5 TEAEs and TEAEs leading to treatment discontinuation, dose modification or death will be summarized by treatment arm, by system organ class (SOC) and preferred term (PT) on the basis of the safety population. Frequencies and percentages of patients experiencing (at least) one event in the respective category will be presented by decreasing frequencies. If patients have more than one AE within a SOC or PT they will be counted only once for the respective SOC or PT. Additionally the total numbers of TEAEs will be provided for each SOC and overall.

Similar summary presentations will be provided for the incidence of TEAEs leading to dose reduction and drug interruption and TEAEs leading to hospitalization.

Non serious Treatment-emergent Adverse Events with >5% frequency will be also presented by SOC and PT. In addition, Serious Treatment-emergent Adverse Events, Fatal serious TEAEs and serious TEAEs related to pirfenidone or placebo will be presented in the same table by SOC and PT.

A summary table presenting the numbers and frequency of patients with TEAEs by most extreme CTCAE Grade (Grade 1, Grade 2, Grade 3, Grade 4 and Grade 5) will be provided for each SOC and PT by treatment arm. In case the most extreme intensity is missing, it will be replaced by the initial intensity. If both most extreme and initial intensity are missing, the AE will be included in the Grade ≥3 category and a category for "missing" will be added.

Further, Kaplan-Meier curves for time to onset of first adverse event of the most relevant related TEAEs will be provided by treatment arm when the number of events are enough to do the analyses. These will include the following PTs or groups of AEs: Nausea, Diarrhoea, Weight decreased, Fatigue, Decreased appetite, and photosensitivity, or rash. In addition, the analysis will be done for the SOC GI.

All adverse event data will be listed by patient number and study day of onset including a flag variable for identifying the period of the event (double-blind treatment period or safety follow-up period). If the AE does not belong to any of the periods, the period flag will be missing.

In addition, for regulatory purpose two additional tables will be provided:

Pirfenidone — F. Hoffmann-La Roche Ltd

Frequency of adverse drug reactions occurring in patients treated with Esbriet (Pirfenidone) in clinical trials

TEAEs from day 1 of dosing until 168 days for MA39189 will be compared with the data from the phase III studies CAPACITY1 and 2 and ASCEND (restricted to first 168 days after first dose). The frequency of patients with related AEs (ADR) will be presented by System Organ Class and will be classified by their occurrences into

- Very common ((>=10% incidence rate)
- common ((>= 1% to <10% incidence rate)
- uncommon (>= 0.1% to <1% incidence rate)
- rare (>= 0.01% to <0.1% incidence rate)

Patients who withdrew from treatment during first 168 days of dosing will be censored at day of withdrawal for this analysis.

Rates of Adverse events per 100 patient years

TEAEs and SAEs from day 1 of dosing until 168 days for MA39189 will be compared with the data from the registrational phase III studies in IPF patients CAPACITY1 and 2 and ASCEND (restricted to first 168 days after first dose). The following parameters will be displayed in this analysis:

- duration of study in patient years (PY), calculated as sum of all patient's observation times).
- number of patients with at least one event,
- number of all events, defined as all AEs from all patients with onset date during observation time period
- rate of events per 100 PYs observation time, calculated as [number of events/duration] * 100
- 95% CI for this rate with
 - o Lower limit = $100*[number of events z_{1-\alpha/2}* SQRT(number of events)]/duration$
 - o Upper limit = 100*[number of events + $z_{1-\alpha/2}$ * SQRT(number of events)]/duration

where $z_{1-\alpha/2}$ is the 1- $\alpha/2$ quantile of the standard normal distribution.

Patients who withdrew from treatment during first 168 days of dosing will be censored at day of withdrawal for this analysis. The analysis will be repeated for all TEAEs/SAEs from first day of dosing until 28 days of last dose, irrespective of the different study durations for MA39189 versus the phase III studies.

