Following treatment initiation, the daily dosage will be titrated to the full dosage of nine capsules per day over a 14-day period as outlined in [Table 2](#) . After the titration period, trial treatment will continue through Week 24 and monitoring will be conducted by site visits. Patients should remain on a stable maintenance dose for the duration of the treatment period unless the dose is reduced or dosing is interrupted to manage an adverse event (see Section [5.1.1](#)). Any patient with an actual or anticipated interruption of trial treatment for a period of ≥ 28 consecutive days will be reported by telephone to Roche's medical monitor or designee to discuss the circumstances of the case. Once the patient restarts trial treatment, the dose must be re-titrated over 14 days as described in [Table 2](#) . A Follow-up Visit will occur 28 days after the end of the 24-week double-blind treatment period.

[figure not shown]
After completion of the double-blind treatment period and the Follow-up Visit at Week 28, the Sponsor will offer the possibility to the patients to receive open-label pirfenidone within the trial protocol in a safety follow-up period of up to 12 months. During the safety follow-up period, the patients should be evaluated by the investigator approximately every 3 months. A final Follow-up Visit will be performed at the end of the safety period, 28 days after the last open-label dose.

Table 2 Titration Schedule

Treatment Days	Dosage
Days 1 through 7	One capsule three times daily with meals
Days 8 through 14	Two capsules three times daily with meals
Day 15 onwards	Three capsules three times daily with meals

The Sponsor will provide trial treatment on a double-blind basis. The design that will be utilized in this trial is shown in [Figure 1](#) .

Figure 1 Trial Schema

¹ Patients will be required to taper and/or discontinue all prohibited medications in the 28 days prior to the start of screening during the washout period. Patients not taking a prohibited medication will forgo the washout period and directly enter screening.

² Informed consent must be documented before any trial-specific screening procedure is performed, and may be obtained either at the Washout or Screening Visits.

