4.2 METHOD OF TREATMENT ASSIGNMENT AND BLINDING

Patients will be randomized 1:1 to receive either pirfenidone versus placebo. The randomization process will be conducted using a validated interactive voice or web-based response system (IxRS). To guard against systematic selection bias and ensure comparability of treatment groups, the randomization will be stratified by concomitant MMF treatment (yes/no), the presence/absence of IPAF as defined by the MDT.

To maintain the double-blind nature of the trial, the pirfenidone and placebo treatments will be identical in appearance (see Section 4.3.1.1).

The investigational site personnel and the patients will be blinded to treatment assignment following randomization. The iDMC and any personnel performing any interim analysis (as applicable) will be unblinded to the treatment throughout the trial.

If unblinding is necessary for patient management (e.g., in the case of a serious adverse event for which patient management might be affected by knowledge of treatment assignment), the investigator will be able to break the treatment code by contacting the IxRS. Treatment codes should not be broken except in emergency situations. The investigator should document and provide an explanation for any premature unblinding (e.g., accidental unblinding, unblinding due to a serious adverse event).

Unblinding should not necessarily result in the withdrawal of a patient from the trial. After unblinding, the patient will be withdrawn from the 24-week double-blind treatment period. If the unblinding was based on the investigator's safety concerns and reveals that the patient had been treated with pirfenidone, the patient will be withdrawn from the trial. In this case, the patient will attend the Early Treatment Discontinuation Visit and thus end his/her participation in the trial. However, if unblinding reveals that the patient had not been treated with pirfenidone and that the investigator has no further safety concerns, then the patient may be offered the option to continue into the 12-month open-label pirfenidone safety follow-up period. In this case, the patient will attend the Early Treatment Discontinuation Visit (± 28 days after the last dose of the double-blind

treatment) and on the same day begin his/her participation in the 12-month open-label pirfenidone safety follow-up period.

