4.3.4 Continued Access to Pirfenidone

After completion of the double-blind treatment period, the Sponsor will offer the possibility to the patients to receive continued access to pirfenidone in a safety follow-up period of up to 12 months, within this clinical trial protocol. A final Follow-up Visit will be performed at the end of the safety period, 28 days after the last open-label dose.

At the end of the 24-week double-blind treatment period, in order to maintain blinding, all patients will discontinue treatment over a 28-day period and return for the Follow-up Visit.

For patients who could benefit from participating in the 12-month safety follow-up period, according to the investigator's judgment, open-label pirfenidone will be started on the 28-day Follow-up Visit, using the titration schedule in [Table 2](#) . During the 12-month safety follow-up period, initially, patients will be evaluated at monthly visits for the first 6 months. At the end of the first 6 months, patients will be evaluated at each site visit occurring approximately every 3 months until the end of the safety follow-up period. In addition, at the end of the first 6 months, patients will perform home pregnancy tests at each month where there is no site visit. Patients will be provided with home pregnancy test kits and will be instructed to contact the site immediately should the test result be positive. In such cases, the patient must visit the site for a confirmatory serum pregnancy test. Refer to Schedule of Assessments for the assessments to be performed during this safety follow-up period ([Appendix 1](#)). The dose of pirfenidone used during the safety follow-up period is in accordance to section 4.3.2.1.

Following the end of the 12-month safety follow-up period, the Sponsor will offer post-trial access to the trial treatment (pirfenidone), free of charge, to eligible patients in accordance with the Roche Global Policy on Continued Access to IMP, as outlined below.

A patient will be eligible to receive Pirfenidone (Esbriet®) after completing the trial if all of the following conditions are met:

- The patient has a life-threatening or severe medical condition and requires continued trial treatment for his or her well-being
- There are no appropriate alternative treatments available to the patient
- The patient and his or her doctor comply with and satisfy any legal or regulatory requirements that apply to them.

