- ^k Only LFTs (AST, ALT, bilirubin, and alkaline phosphatase) will be conducted at these visits. During the Safety Follow-up period, LFTs will be performed every month during the first 6 months and subsequently at each visit occurring approximately every 3 months thereafter, until the end of this period.
- ^l All women of childbearing potential will have a serum pregnancy test at screening. Urine pregnancy tests will be performed at the specified subsequent visits. If a urine pregnancy test is positive, it must be confirmed by a serum pregnancy test. During the Safety Follow-up period, urine pregnancy tests will be performed every month during the first 6 months at each site visit. Urine pregnancy tests will continue to be performed on a monthly basis during the remainder of the Safety Follow-up period with patients performing the test at home (using kits provided by the site) during months where there is no site visit and at each site visit occurring approximately every 3 months. Patients will be instructed to contact the site immediately in case the result of the home pregnancy test is positive. In such cases, the patient must visit the site for a confirmatory serum pregnancy test.
- ^m Open-label treatment with pirfenidone will be started at this visit, if the patient requests continued treatment with pirfenidone.
- ⁿ Handheld spirometry will be conducted by the patient every day in a seated position.
- ^o To provide handling evaluations and quality assurance for the daily spirometer assessments, nursing visits to the patient's home (or at another suitable location) will occur at least three times during the trial, namely between Weeks 1 and 4, between Weeks 8 and 12, and between Weeks 16 and 20. Additional home nursing visits may be conducted according to the investigator's judgment.
- ^p 6-Minute Walk Distance (6MWD) is used to evaluate the functional capacity of patients with lung disease.
- ^q Questionnaires will be self-administered prior to the patient receiving any information on disease status and prior to the performance of non-PRO assessments. Refer to [Appendix 2](#) for copies of the questionnaires and a brief description.
- ^r Includes any medication (e.g., prescription drugs, over-the-counter drugs, vaccines, herbal or homeopathic remedies, nutritional supplements) used by a patient from the washout period until 28 days after the last dose of trial treatment.

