4.7 SAFETY FOLLOW-UP ANALYSES

Data collected during the safety- follow-up period will be analyzed in the following way.

Adverse events during the 12-month safety follow-up period for pirfenidone treatment will be defined as:

 AEs that started or worsened on or after the date of safety follow-up period start until the end of the safety follow-up.

Pirfenidone — F. Hoffmann-La Roche Ltd

The safety follow-up population will be used for these analyses.

Summary tables for the incidence of AEs, related AEs, serious AEs, related serious AEs, severe AEs and severe related AEs will be summarized by system organ class (SOC) and preferred term (PT). Frequencies and percentages of patients experiencing (at least) one event in the respective category will be presented by decreasing frequencies. If patients have more than one AE within a SOC or PT they will be counted only once for the respective SOC or PT. Additionally, the total numbers of AEs will be provided for each SOC and overall. As with the end of the double-blind treatment period, an overview of safety will also be presented.

Pirfenidone exposure during safety-follow-up will be analyzed in a similar fashion as described in Section 4.7.1 with regard to treatment duration and amount of drug intake.

Data of laboratory assessments (AST, ALT, bilirubin, and alkaline phosphatase) and vital signs during safety-follow-up period will be analyzed in a similar fashion as described in Section 4.7.4 and Section 4.7.5.

Data will be presented by randomized treatment labeled as 'Randomized Pirfenidone' and 'Randomized Placebo'.

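### The double-blind safety window is not cut at the first open-label dose, so a few days on open-label pirfenidone can be attributed to the randomised arm, including placebo

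*SAP*

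**What the plan says.** All SAP references are to version 3.0.

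**Double-blind period.** SAP 4.6.2 counts as treatment-emergent "AEs that started or worsened on or after first intake of randomized treatment until last positive dose of randomized treatment + 28 days". SAP 4.2 sets the same limit for drug safety generally ("until the date of last positive dose of randomized treatment plus 28 days"). SAP 4.2.4 repeats it for on-treatment assessments, and SAP 4.6.3 uses a 28-day limit for deaths. None of these mentions the first open-label dose.

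**Open-label start.** Protocol 3.1: "A Follow-up Visit will occur 28 days after the end of the 24-week double-blind treatment period". Protocol 4.3.4: "open-label pirfenidone will be started on the 28-day Follow-up Visit, using the titration schedule". Appendix 1, footnote m, agrees: "Open-label treatment with pirfenidone will be started at this visit, if the patient requests continued treatment with pirfenidone". The schedule allows ±5 days for that visit.

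**Follow-up period.** SAP 4.7 counts "AEs that started or worsened on or after the date of safety follow-up period start" and presents the results by randomised arm. SAP 4.2.5 starts the period at the first positive pirfenidone dose after the 28-day visit, and only for patients who completed double-blind treatment. SAP 4.1.4 defines the follow-up population by a dose taken later than end of randomised treatment plus 28 days.

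**Early-unblinded patients.** Under Protocol 4.2, a patient found not to have received pirfenidone may start open-label treatment on the day of the "Early Treatment Discontinuation Visit (± 28 days after the last dose" visit. Appendix 1, footnote b, times that visit at 28 (±5) days.

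**The concern.** The two event periods are meant to be separate but are not mutually exclusive. The double-blind window includes day 28, open-label treatment can begin on or before day 28, and follow-up events count from the first open-label dose. An event after that dose but within 28 days of the last randomised dose meets both definitions.

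For a former placebo patient, this puts an event that occurred on pirfenidone into the placebo column of the randomised safety comparison. SAP 4.6 names related Grade 3 or higher events as the main safety interest, so the attribution rule should be clean. The period flag in SAP 4.6.2 does not settle it: the text covers an event that belongs to neither period, but gives no rule for one that belongs to both.

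**Working it through.** **Inputs**
- Week 24 is Day 168 and the Follow-up Visit is Day 196, each ±5 days (Protocol Appendix 1).
- The double-blind window ends at last positive dose + 28 days, inclusive (SAP 4.2, 4.2.4, 4.6.2).
- The first open-label dose is on the Follow-up Visit day (Protocol 4.3.4).
- Planned patients per arm: 125 (Protocol 6.1).

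**Plan's own figure.** 168 + 28 = 196, so the nominal visit falls exactly on the last day of the window when the last dose is on Day 168.

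**Formula.** Let d be the days from last randomised dose to first open-label dose. Overlap = max(0, 28 − d + 1). Uncovered gap = max(0, d − 29).

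| d | 23 | 24 | 25 | 26 | 27 | 28 | 29 | 30 | 31 | 32 | 33 |
|---|---|---|---|---|---|---|---|---|---|---|---|
| Overlap (days) | 6 | 5 | 4 | 3 | 2 | 1 | 0 | 0 | 0 | 0 | 0 |
| Gap (days) | 0 | 0 | 0 | 0 | 0 | 0 | 0 | 1 | 2 | 3 | 4 |

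**On schedule.** A last dose on Day 168 gives d = 28 and one shared day. The schedule marks no treatment administration at Week 24. If the last dose is on Day 167, the window ends on Day 195, d = 29 and there is no overlap.

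**Extreme reading.** Suppose both visits are anchored to Day 1 and the last dose is taken at the Week 24 visit. The last dose then falls on Days 163–173 and the Follow-up Visit on Days 191–201. The smallest d is 191 − 173 = 18, giving 28 − 18 + 1 = 11 shared days. The largest d is 201 − 163 = 38, with no overlap.

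**Exposure affected.** The documents give no visit-timing or uptake data, so these are assumptions.
- With d uniform on 23–33, 6/11 = 55% of entrants have some overlap. The mean is (6+5+4+3+2+1)/11 = 21/11 = 1.9 days.
- With 50–100% uptake among 125 placebo patients: 125 × 0.5 × 21/11 = 119 to 125 × 1.0 × 21/11 = 239 patient-days.
- Against 125 × 196 = 24,500 placebo patient-days, this is 0.5–1.0%.
- If every entrant started at d = 23: 125 × 0.5 × 6 = 375 to 125 × 6 = 750 patient-days, or 1.5–3.1%.

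**Check of the fix.** If the window ends at min(28, d − 1), the overlap is zero for every d from 18 to 38.

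**The case against.** The strongest reply is that this is a boundary detail. Open-label entry is optional. The usual overlap is a few days at most, and on the ±5-day reading those days lie within the one-capsule titration week (Protocol Table 2). No formal safety testing is planned. The periods are reported in separate tables, and each event in the listing carries one period flag. Patients randomised to pirfenidone re-titrate at the same visit, so their arm keeps such events too.

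Much of this stands, and it limits the size. It does not remove the fault: separate tables do not stop an open-label event entering the placebo column, and the flag has no rule for an event in both periods.

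A reader might infer more than the documents support:
- **That every patient overlaps by a day.** This needs open-label entry and, on schedule, a last dose on Day 168.
- **That 11 days is typical.** It needs a late last dose and an early visit only 18 days apart, whereas Protocol 3.1 and 4.3.4 describe a 28-day interval.
- **That early-unblinded patients overlap by up to 28 days.** This rests on the ±28-day wording in Protocol 4.2, which conflicts with footnote b.
- **That events are double-counted in one table.** Duplication is possible only across the double-blind and follow-up tables. For early-unblinded patients even that is unclear, because SAP 4.2.5 covers completers only.
- **That the safety difference is shown to narrow.** The net effect cannot be derived from the documents. The first-month fatigue figure in Protocol 5.1.1.6 (81/162) is a share of pirfenidone patients who reported fatigue, and it does not describe the first six days.

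**Conclusion.** The point holds as a small attribution error in the stated rule. An event starting after the first open-label dose can be assigned to the randomised arm when that dose falls on or before day 28, and for completers it can also appear in the follow-up tables. The main consequence is a slightly blurred placebo safety profile. The affected share of placebo patient-days rests on the timing and uptake assumptions shown above; the number of events it would move cannot be calculated from the documents.

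The reverse problem matters too. When the visit is late, events of patients who go on to open-label treatment can fall in neither period, because the post-treatment category in SAP 4.6.2 is limited to patients who do not enter follow-up.

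The SAP 4.6.2 event-rate analysis repeated to 28 days after last dose shares the overlap. The first-168-day tables are essentially unaffected.

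**What to change.** 1. **Events and deaths (SAP 4.2, 4.6.2, 4.6.3).** Count onset up to the earlier of last positive randomised dose + 28 days and the day before the first open-label dose. An event on the first open-label day then belongs to follow-up. This matches SAP 4.2.2, which treats events on the first randomised dosing day as treatment-emergent.
2. **One period per event.** State that the period flag is exclusive and drives both sets of tables.
3. **Gap days.** State where an event goes if it starts after day 28 but before the first open-label dose.
4. **Assessments (SAP 4.2.4).** Cut at the first open-label dose, but keep visit-day pre-dose assessments as double-blind. A day-before cut would discard the scheduled Week 28 ECG and vital signs.
5. **Alignment.** Bring SAP 4.1.4, 4.2.5 and 4.7 into line with Protocol 4.3.4, which starts dosing on the visit day while SAP 4.2.5 counts from after the visit. State which period covers early-unblinded patients. Protocol 4.2 and Appendix 1 footnote b must be reconciled on the timing of the discontinuation visit.

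**Cost.** A few clauses. SAP 4.5.8 records that the primary analysis was performed in March 2019, so affected safety tables must be rerun, and a few boundary-day events will change period.
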